4. STUDY PROCEDURES AND FLOWCHART

Table 4.1.1-Part 1 Schedule of Events

	Screening ¹	Baseline Visit 1	Visit 2	Visit 3	Visit 4	Visit 5	Visit 6	Visit 7	ET Visit 8 ²	Safety Follow- Up Visit 9
Evaluation	Day -7 to -1	Week 1 Day 1	Week 1 Day 2	Week 4 ± 3 days	Week 8 ± 3 days	Week 12 ± 5 days	Week 16 ± 3 days	Week 20 ± 5 days	Week 24 ± 5 days	Week 28 ± 3 days
Evaluation	Site Visit	Site Visit	Site Visit	Home Visit	Home Visit	Site Visit	Home Visit	Site Visit	Site Visit	Home Visit
Informed consent / assent	Х									
Eligibility review	Х	X								
Demographics / medical history	Х									
Concomitant medications	Х	Х	X	Х	Х	Х	Х	Х	Х	Х
Adverse events	Х	X	Х	Х	Х	Х	Х	Х	Х	Х
Urinalysis/ urine pregnancy test ³	Х	Х				Х		Х	Х	
12-Lead ECG	Х	Х				Х		Х	Х	
Vital Signs	Х	Х	Х			Х		Х	Х	
Physical exam ⁴	Х	Х	Х			Х		Х	Х	
Dermatologic exam	Х	Х	Х	Х	Х	Х	Х	Х	Х	Х
Digital photography ⁵		Х		X ⁶	X ⁶	Х	X ⁶	Х	Х	X ⁶
VIIS (Investigator- assessed)		Х	Х			Х		Х	Х	
Global impression of severity		Х				Х		Х	Х	
Patient/Observer- reported scales ⁷		Х				Х		Х	Х	
PD sample collection ⁸		Х				Х		Х	Х	
Clinical laboratory testing ⁹	х	Х		Х		Х		Х	Х	
PK sample collection ¹⁰		Х	Х			Х		Х	Х	
Randomization		Х								
Administer study drug		X ¹¹	Х	Х	Х	X ¹¹	Х	X ¹¹	Х	
Dispense study drug & diary			Х			Х		Х		

Syneos Health #1009367

diary

ET = early termination; ECG = electrocardiogram; PD = pharmacodynamic; PK = pharmacokinetic; VIIS = Visual Index for Ichthyosis Severity

- 1. Samples collected for urinalysis and clinical laboratory tests may be analyzed at a local lab.
- 2. Subjects who terminate early from the study will not require post-dose assessments at Visit 8 (Week 24).
- 3. Urine pregnancy test for female subjects of child-bearing potential only. Test can be analyzed at the study site.
- 4. Complete physical exam, including height and weight collection, performed at Screening Visit only; symptom-directed physical exams at all other timepoints.
- 5. Subjects should refrain from bathing and applying study drug or as-needed topical symptom control therapy (emollients) to the treatment area within 12 hours of obtaining digital photographs.
- 6. During at-home visits, photographs will only be taken if there are any safety concerns.
- 7. Patient/Observer-reported scales to be administered: EQ-5D-5L, global impression of severity, global impression of bother, global impression of treatment, itching, scratching, burden of bathing/showering, and Children's Dermatology Life Quality Index (CDLQI) / Dermatology Life Quality Index (DLQI).
- 8. PD assessments include skin cell samples and transepidermal water loss (TEWL) procedures.
- 9. Clinical laboratory includes hematology and chemistry. Refer to Sections 6.15.1 and 6.15.2 in the study protocol, for more detail.
- 10. PK collection includes blood and urine samples.
- 11. Study drug will be administered daily. At study visits when PK samples are collected, study drug may be administered at the study clinic after pre-dose PK samples have been obtained. At Visit 1, Investigator should apply study drug to the initial treatment area (~20% BSA) during the visit. At Visit 2, study drug may be applied to the initial treatment area during the visit (after pre-dose PK sample collection) by the Investigator or subject/caregiver. At Visit 5, if the treatment area is expanded to up to 45% BSA, the Investigator should apply study drug to the treatment area. At Visit 7, if the treatment area is expanded to up to 90% BSA, Investigator should apply study drug to the treatment area.

Table 4.1.2-Part 1 Pharmacokinetic and Cardiac Monitoring

Visit			Visit 1			Visit 2	Visits 5, 7 and 8				
Time (hours)	Pre-Dose	1	2	4	8	24	Pre-Dose	1	2	4	8
Window		± 15 min	± 15 min	± 15 min	± 15 min	± 60 min	-	± 15 min	± 15 min	± 15 min	± 15 min
Adults (age ≥ 12 years old)											
12-Lead ECG	X	X	X	X	X		X	Х	X	X	X
Vital Signs	×	×	X	×	X	X	X	X	X	×	X
Blood PK Samples	X	X	X	X	X	X	X	Х	X	X	X
Urine PK Samples	×				Х		X				X
Children (age < 12 years old)											
12-Lead ECG	X	X		X			X	X		X	
Vital Signs	×	×		×		X	×	X		×	
Blood PK Samples	×	×		×		X	X	X		X	
Urine PK Samples	Х			X			Х			X	

Statistical Analysis Plan

Aldeyra Therapeutics Protocol # ADX-102-SLS-006

Version 1.0

Syneos Health #1009367

5. STUDY OBJECTIVES

5.1. PRIMARY OBJECTIVE

To evaluate the efficacy of ADX-102 1% topical dermal cream on ichthyosis associated with SLS.

5.2. SECONDARY OBJECTIVE(S)

To evaluate the safety and secondary efficacy endpoints of ADX-102 1% topical dermal cream in subjects with SLS.

5.3. DETERMINATION OF SAMPLE SIZE

Part 1 of the clinical trial will assess the effect size on the VIIS scaling score with ADX-102 1% topical dermal cream, and will confirm the sample size needed for Part 2. Unblinded Part 1 safety and efficacy results will be available to the Sponsor for administrative consideration and use upon completion of Part 1. Efficacy data will be used to confirm the sample size estimation for Part 2 as well as to perform between groups and within group descriptive and inferential statistical analyses

5.4. SUBJECT NUMBERING

Each subject screened for the clinical trial will be assigned a unique subject number that will be used to identify the subject throughout their participation in the clinical trial. If a subject fails to be randomized, the reason should be documented in the source documents and case report form (CRF). The subject will be considered a screen failure.

5.5. RANDOMIZATION AND BLINDING

Subjects will be randomized 2:1 to receive ADX-102 1% or vehicle through interactive response technology (IRT) at Baseline Visit Day 1.

Subjects will be randomized in a double-blind fashion. Investigators, qualified study personnel, subjects, and caregivers will be blinded to the study drug treatment administered. The Sponsor will also be blinded to the study drug treatment administered until database lock.

In the event a replacement of a subject is required (see Section 4.3 in the protocol), the next available subject number will be assigned to either ADX-102 or vehicle based on the randomization scheme.

Syneos Health #1009367

In the event that randomization assignment results in an active to vehicle ratio of less than 2:1 then the clinical trial may be extended until the ratio is achieved per sponsor discretion.

5.6. EMERGENCY UNBLINDING

Emergency unblinding should only be performed when necessary to treat the subject. Most often, knowledge of the possible treatment assignments is sufficient to treat a subject who presents with an emergency condition.

Unblinding will result in the subject being discontinued from the clinical trial, irrespective of whether the Investigator the event is deemed related to study drug.

The treatment code for a subject may only be broken by the Investigator or Sponsor for reasons of subject safety or in an emergency when knowledge of the study drug administered would be important for the treatment of the patient. However, the Investigator should make every effort to contact the Medical Monitor to discuss the emergency and the need to unblind, prior to unblinding any subject. Please refer to the Safety Management Plan (SMP), Version 1.0, dated April 12, 2018.

The blind may be broken in the case of a pregnancy should the subject desire this information.

The date, time and reason for breaking the blind are to be recorded in the subject's CRF and source documents.

In the event of a drug-related, serious, unexpected AE, the Sponsor's Unblinded Pharmacovigilance Department or designee will be provided with the treatment assignment for the subject for regulatory reporting (detailed process outlined in ADX-102-SLS-006 Safety Monitoring Plan).

5.7. ADMINISTRATION OF STUDY MEDICATION

A standard amount of study drug for the percent BSA under treatment will be measured and applied to the treatment area once daily to achieve a dose of approximately 8 mg/cm2, with each application administered approximately 24 hours apart. Study drug should only be administered to the treatment area, as directed by the Investigator, during the clinical trial.

The Target Efficacy Area used for the primary endpoint assessment in Part 1 will be based on one of the body sites as defined in the VIIS tool (upper back, upper arm or lower leg/shin) that has a VIIS scaling score of Grade 2 or higher as assessed by the Investigator. The body site with the worst VIIS scaling score should be selected, if applicable. The target efficacy area will be used for all efficacy analyses; for all other treated areas, data will be summarized.

Syneos Health #1009367

The Treatment Area will be determined by the Investigator as follows:

In Part 1, the initial treatment area will be defined as approximately 20% BSA with Grade 2 or higher on the VIIS scaling score, on one-half of the body, left or right side, and will include the target efficacy area. From Week 1 through Week 12, study drug will be applied in the initial treatment area.

If the Investigator determines that there are no safety or tolerability issues at the end of Week 12, the treatment area will increase to all of the affected areas of ichthyosis on one-half of the body (approximately 40-45% BSA in a typical SLS patient), left or right side. From Week 13 through Week 20, the study drug will be applied to the extended treatment area affected by ichthyosis.

If there are still no safety or tolerability issues at the end of Week 20, the treatment area will further increase to all affected areas of ichthyosis on the entire body (approximately 80-90% BSA in a typical SLS patient). From Week 21 through Week 24, the study drug will be applied to the entire body affected by ichthyosis.

For example, if the left lower leg is determined by the Investigator to be the target efficacy area, then the entire left leg would likely be defined as the initial treatment area. At the end of Week 12, if there are no safety or tolerability issues, the treatment area would extend to the entire left side of the body. At the end of Week 20, if there are no safety or tolerability issues, the treatment area would include the entire body.

Syneos Health #1009367

6. ENDPOINTS

All endpoints will be based on an evaluation period spanning Day 1 through Week 24 in Part 1.

6.1. PRIMARY EFFICACY ENDPOINT

The primary efficacy endpoint is the Visual Index for Ichthyosis Severity (VIIS) scaling score as assessed by the Investigator in the target efficacy area.

6.2. SECONDARY EFFICACY ENDPOINTS

Secondary endpoints include:

VIIS score

- VIIS erythema score as assessed by the Investigator in the target efficacy area
- VIIS scaling score as assessed by a central reader in the target efficacy area
- VIIS erythema score as assessed by a central reader in the target efficacy area

Clinical Outcome Assessments

- EQ-5D-5L
- Clinician global impression of severity
- Patient/Observer global impression of severity
- Patient/Observer global impression of bother
- Patient/Observer global impression of treatment
- Patient-reported itching
- Patient/Observer-reported scratching
- Patient/Observer Burden of bathing/showering
- Children's Dermatology Life of Quality Index (CDLQI) / Dermatology Life Quality Index (DLQI)

Biomarker Parameters

Transepidermal Water Loss (TEWL)

Exploratory Biomarker Parameters

Lipid biomarkers from skin cells

All analyses involving lipid biomarkers will be considered exploratory and will be conducted post-hoc.

6.3. PHARMACOKINETIC ENDPOINTS

Full pharmacokinetic (PK) profile on Day 1 and at steady state following treatment up to 90% BSA. Planned analysis detailed in separate PK analysis plan.

Syneos Health #1009367

6.4. CLINICAL OUTCOMES ASSESSMENT ENDPOINTS

Clinical Outcomes Assessments are collected at predefined study visits. Data will be analyzed per a separate Clinical Outcomes Assessments Analysis plan.

6.5. SAFETY ENDPOINTS

The safety endpoints include dermatological endpoints, vital sign measurements, physical examinations, hematology and chemistry laboratory testing, ECG readings, use of concomitant medications, and adverse events.

6.6. PLANNED ANALYSES

The following analyses will be performed for the ADX-102-SLS-006 Phase 3 clinical trial Part 1:

- Analyses for the Data Safety Monitoring Board (DSMB)
- Analysis of unblinded data following completion of Part 1

All safety and efficacy data collected from the approximately 9 subjects will be analyzed upon completion of Part 1.

Syneos Health #1009367

7. ANALYSIS POPULATIONS

7.1. ENROLLED POPULATION

The enrolled population will include all patients who gave informed consent to participate in the clinical trial.

7.2. SAFETY POPULATION

The Safety Population (SAF) consists of all randomized subjects who use at least one dose of study drug, regardless of whether they undergo any clinical trial assessments. Patients will be included in the treatment group corresponding to the study treatment they actually received for the analysis of safety data. The SAF will be used for the analysis of safety data for this clinical trial.

7.3. MODIFIED INTENT-TO-TREAT (M-ITT) POPULATION

The modified-Intent-to-Treat (m-ITT) Population will include all randomized subjects from the SAF who received at least one dose of study drug and have at least one VIIS assessment post visit 2. Subjects will be analyzed according to randomized treatment. Unless otherwise specified, efficacy analysis will be performed on this population.

7.4. PER PROTOCOL POPULATION

The Per-Protocol Population (PPP) will include the patients from the m-ITT population who had no major protocol deviations that could impact the efficacy analysis. The list of protocol deviations that may exclude a patient from the PPP will be reviewed and approved by the sponsor prior to database lock.

Patients could be excluded from the PPP if:

- Subjects did not receive study drug as assigned
- Subject did not meet all inclusion/exclusion criteria
- The final determination on major protocol deviations and potential impact on efficacy parameters and thereby the composition of the PPP, will be made prior to the unblinding of the database and will be documented separately.

Regardless of randomized treatment group, patients will be included in the analysis group based on the treatment actually received for the analysis of efficacy data using the PPP.

Due to the small sample size in Part 1, efficacy analysis will not be conducted on PPP.

Syneos Health #1009367

7.5. PHARMACOKINETIC (PK) POPULATION

The PK Population will include all subjects who received at least one dose of study drug and have at least one measured post-dose PK concentration in plasma or urine. The PK Population will be used for the analysis of all PK data.

7.6. PROTOCOL DEVIATIONS

Possible protocol deviations will be identified and displayed in a data listing, sorted by subject and clinical trial site (where applicable). Protocol deviations will be evaluated at the data review meeting (DRM), prior to database lock (DBL), to determine protocol deviations considered to have significant impact on patient safety, efficacy or the validity of the data. Patients with protocol deviations may be excluded from the per protocol population if the deviation has an impact on the efficacy analysis.

Syneos Health #1009367

8. GENERAL ASPECTS FOR STATISTICAL ANALYSIS

8.1. GENERAL METHODS

All patients entered into the database will be included in patient data listings. Summary tables will be provided for all patients.

Unless otherwise specified, all demographic, baseline and safety data will be presented by treatment arm and overall. Efficacy data will be presented by treatment arm.

Quantitative (continuous) data - absolute values and changes from baseline, where appropriate - will be summarized with number of observations (n), mean, standard deviation (SD), median, minimum, and maximum and 1st and 3rd quartiles for efficacy tables only.

Qualitative (categorical) data will be summarized using number of observations (n), and frequency and percentages of patients. Unless stated otherwise, the calculation of percentages will be based on the total number of patients with non-missing data in the set of interest.

Comparisons will contrast outcomes between time points within both ADX-102 1% and Vehicle treatment groups as well as contrast outcomes between each of these treatment groups.

- All primary and secondary efficacy analyses will be performed on the m-ITT population.
- The safety analysis will be performed on the SAF population.

Summary tables will include outcomes for a given treatment at a given time point, the between group differences in change from baseline at each time point, and the within group difference at each time point.

8.2. CONTINGENCIES DUE TO LIMITATIONS INHERENT IN SLS RESEARCH

There will be no adjustment for multiplicity in the analyses of primary and secondary endpoints. The limitations of achieving statistical power due to the limited availability of subjects as well as the longevity and consistency of SLS symptoms make statistical significance difficult to achieve.

In this Phase 3 clinical trial, efficacy decisions must rely upon a clearly observable trend in change in skin scaling, a socially stigmatic symptom of great discomfort that absent a novel treatment will require an inordinate amount of attentiveness on a daily basis for the life of the patient. Thus, significance levels are provided in this clinical trial as an additional index of change rather than an inferential expectation.

Syneos Health #1009367

If warranted by observed data characteristics relative to model assumptions, non-parametric methods and small sample statistical methods may be substituted for one or more of the below anticipated model based analyses. The rationale for any such change will be provided.

Finally, if statistical power is materially increased through the addition of one or more continuous or stratification covariates to a statistical model described in this SAP, the model will include the covariate(s). Analogously, if stratification adds power to a non-parametric or small sample procedure, the analysis will include stratification.

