- 7. Subject has a history of any malignancy.
- 8. Subject is known to be human immunodeficiency virus positive or had other known immunodeficiency.
- 9. Subject has any clinically significant laboratory test abnormalities or a history of any other condition that, in the opinion of the Investigator, could compromise the subject's ability to comply with the protocol or that could compromise the subject's safety or the interpretation of the study results.
- 10. Subject is currently participating in any other therapeutic clinical study.
- 11. Subject is pregnant or lactating.

Statistical Analysis:

Part 1 and Part 2 will be analyzed in a similar fashion with the exception that the Part 1 analysis will include a sample size evaluation. Part 1 analyses in some instances may be confined to the descriptive aspect of the evaluation (i.e., inferential p-values may be omitted) due to the small sample size of 6 treated and 3 control patients.

The primary efficacy endpoint (VIIS scaling severity as assessed by the Investigator in the target efficacy area) as well as all secondary efficacy variables that are captured on a continuous or semi-continuous

scale

will be expressed as baseline to ending change scores. Two-sided 95% confidence intervals (CIs) will be computed and used descriptively for all variables but also to evaluate change relative to a standard for some variables (i.e., by determining whether the CI includes or excludes the standard).

The two-sided 95% CI for VIIS scaling severity will be used to evaluate the primary endpoint as follows. An efficacy claim from Part 2 will be made if: 1) the lower confidence interval is above zero, 2) the midpoint of the confidence interval is at least 0.5 units is size, and 3) at least 50% of subjects have favorable change scores of one or greater.

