10.1 Sample Size

Part 1 of the study will assess the effect size on the VIIS scaling severity score with ADX-102 1% topical dermal cream, and will confirm the sample size needed for Part 2. Part 2 is expected to require approximately 30 subjects.

The approximate number of 30 subjects for Part 2 was based on the NS-003 Phase 2 study which used the ISS endpoint. The mean ISS Scaling sub-score change from baseline was -0.7 with a standard deviation of 0.52. Conservatively, the change was set to -0.5 and the standard deviation to 0.6. A sample size of 20 achieves 94% power to detect a difference of 0.5 between the null hypothesis mean of 0.0 and the alternative hypothesis mean of -0.5 with an estimated standard deviation of 0.6 and with a significance level (alpha) of 0.05 using a two-sided one-sample t-test. If the above assumptions remain, except that the standard deviation is increased to 0.7, then a sample size of 20 achieves a power of 85%. The sample size of 30 is therefore based on these estimates requiring 20 subjects to be treated with ADX-102 1%. As subjects will be randomized in a 2:1 ratio, 10 subjects will be treated with vehicle.

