10.1. PRIMARY EFFICACY ENDPOINT AND ANALYSIS

The primary endpoint for the clinical trial is change from baseline in the VIIS scaling score in drug-treated subjects, as assessed by the investigator, in the target efficacy area. The VIIS provides five-point Likert scales (range 0-4) for erythema and scaling that increases in severity with increasing score values.

The target efficacy area for all efficacy analyses will be one of the body sites as defined in the VIIS tool (with the exception of Dorsal foot) with Grade 2 or higher on baseline VIIS scaling score as assessed by the Investigator.

The within-group change from baseline will be the primary focus of interest in the primary analysis.

Syneos Health #1009367

Primary Analysis

A Mixed Model Repeated Measures (MMRM) model will be used to perform the primary analysis of the VIIS scaling score in drug-treated subjects (not vehicle-treated subjects). Change from baseline VIIS scaling score will serve as the dependent variable. The model will include the baseline value (Visit 1) as a covariate (if useful) and visit (treated as a factor; the visit term will cover Visit 1, 5, 7, and 8). An unstructured covariance structure will be assumed and a Type III model will be evaluated. If the unstructured covariance structure matrix results in a lack of convergence, then Toeplitz (TOEP), first-order autoregressive (AR1), compound symmetric (CS) covariance structure will be used in that order. If the MMRM model cannot hit convergence with any correlation structure, then a within-subject t-test (baseline-adjusted, if useful) will be used to compare baseline to Visit 8. It should be noted that improvement will be signified by the existence of a negative change score.

The primary efficacy endpoint will be summarized descriptively by visit and across all visits. The table will contain descriptive statistics on observed values and change from baseline at each time point.

The primary analysis using the MMRM model will be summarized in a consolidated table containing the following:

- Descriptive statistics for change scores at baseline and each post-treatment time point.
- The LS mean change scores with accompanying standard errors and 95% confidence intervals for each visit.
- Within-group contrasts for each given visit.
- Significance levels for the visit effects.

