Along with the table detailing the results of the MMRM model, a consolidated table presenting the essential information for the primary analysis will be constructed. The primary endpoint will be deemed to have been met if the Visit 8 (week 24) term is significant, and the term coefficient is negative.

Secondary and Sensitivity Analyses Related to the Primary Outcome Variable

The following analyses will be performed to provide additional insight into VIIS scaling.

Responder Analysis

For drug-treated subjects, responder status will be assigned to a subject if at a given post treatment time point an improved change from baseline of at least 1 VIIS scaling

Syneos Health #1009367

unit occurs. A Generalized Estimating Equation (GEE) model will be used to evaluate the predicted log odds, odds and probability of response. The model will include the effect of visit (treated as a factor). An unstructured covariance structure will be assumed and a Type III model will be evaluated. If the unstructured covariance structure matrix results in a lack of convergence, then first-order autoregressive (AR1) and compound symmetric (CS) covariance structure will be used in that order.

Results will be captured in a consolidated table that contains the following information:

- Number and percent of observed responders and non-responders at all post-treatment time points;
- Significance levels for the visit effects;
- The model predicted log odds, odds and probability of response with standard errors and 95% confidence intervals for each visit;
- Within-group contrasts expressed as an odds ratio, accompanied by a 95% confidence interval.

AUC Analysis

For drug-treated subjects, AUC for change from baseline over all post-treatment time points will be calculated for each subject using the trapezoidal rule. A linear model comparing AUC to zero (no change from baseline) will be performed.

Survival Analysis

For drug-treated subjects, time to first response (i.e., a one-unit VIIS scaling improvement) will be captured in a Kaplan Meier plot. A hazard rate estimate will be generated.

Analysis for Patients Experiencing one or more Treatment interruptions

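### SAP 8.2 lets an unnamed test replace the Part 1 primary analysis on the strength of the observed data; with about six treated subjects, that choice can flip the 'met' verdict

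*SAP*

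**What the plan says.** SAP 10.1 tests change from baseline in the Investigator's VIIS scaling score in drug-treated subjects only. It starts with an MMRM with unstructured covariance. If that fails to converge, Toeplitz, AR(1) and compound symmetry follow in that order. If none converges, "then a within-subject t-test (baseline-adjusted, if useful) will be used to compare baseline to Visit 8". Every step is triggered by non-convergence and nothing else. The endpoint is then declared met "if the Visit 8 (week 24) term is significant, and the term coefficient is negative". That sentence gives neither alpha nor sidedness.

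SAP 8.2 opens a second route with a different trigger. "If warranted by observed data characteristics relative to model assumptions", it says, "non-parametric methods and small sample statistical methods may be substituted for one or more of the below anticipated model based analyses". The only condition is procedural: "The rationale for any such change will be provided". The same section says that "significance levels are provided in this clinical trial as an additional index of change rather than an inferential expectation".

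The Synopsis of the protocol allows for Part 1 inference being limited "due to the small sample size of 6 treated and 3 control patients". SAP 8.3 nonetheless keeps inferential statistics for the primary analysis, and SAP 12 describes the end-of-Part-1 analysis as fully unblinded.

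**The concern.** The two sections give different rules for the same analysis. Section 10.1 is an ordered, mechanical sequence. Section 8.2 allows a judgement about distribution to override it, with no named replacement and no date by which the judgement must be made. The primary model uses only treated subjects, so its assumptions can be checked on the relevant data only once treatment codes are known. About six change scores on a five-point scale will always leave room to question normality.

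The success rule does not fit the replacement either. It asks for a model term and a coefficient, and a rank or sign-flip test has neither. The t-test fallback in 10.1 has no Visit 8 term either, so the rule needs wording for both.

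If different admissible tests give different answers on likely data, the declared Part 1 result depends on a choice made after looking. Because 8.2 authorises the swap in advance, it might also escape the post-hoc label that SAP section 2 requires for additional analyses.

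**Working it through.** **The plan's own figure.** Protocol 10.1 gives 94% power (SD 0.6) and 85% (SD 0.7) for n=20, difference 0.5, two-sided one-sample t-test at 0.05. With noncentrality 0.5/SD × √20 (3.73 and 3.19) and 19 df, I get 94.2% and 85.8%. Both reproduce, the second apparently truncated. No power is stated for the Part 1 test.

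**Inputs.** Six treated subjects (Protocol Synopsis; the total of nine is approximate). Whole-grade changes, inferred from the 0–4 five-point scale in SAP 10.1. Two-sided alpha 0.05, an assumption carried over from Protocol 10.1.

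**Formulas**, for k of six subjects at −1 and the rest at 0:
- t = mean / (SD/√6), 5 df. This equals the MMRM Visit 8 contrast only with complete data, unstructured covariance and no covariate.
- Exact two-sided signed-rank, sign or sign-flip test: p = 2/2^k.
- Asymptotic signed-rank, tie-corrected, no continuity correction: with all k ranks tied, |z| = √k.

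| At −1 / at 0 | Mean (SD) | t | p, t-test | p, exact | p, asymptotic |
|---|---|---|---|---|---|
| 6 / 0 | −1.000 (0) | undefined | undefined | 0.031 | 0.014 |
| 5 / 1 | −0.833 (0.408) | −5.00 | 0.0041 | 0.0625 | 0.025 |
| 4 / 2 | −0.667 (0.516) | −3.16 | 0.025 | 0.125 | 0.0455 |
| 3 / 3 | −0.500 (0.548) | −2.24 | 0.076 | 0.25 | 0.083 |

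With a continuity correction, the asymptotic values for 5/1 and 4/2 become 0.037 and 0.072, so even that detail changes the 4/2 verdict.

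**Link to Phase 2.** Protocol 10.1 reports: "The mean ISS Scaling sub-score change from baseline was -0.7 with a standard deviation of 0.52". If this describes the six active subjects (12 randomized 1:1, Protocol 1.3.1) and ISS was scored in whole grades, the only set that fits is four at −1 and two at 0. Repeating that pattern would be met by t-test and not met by an exact test. The section states neither the n nor the scoring step, and ISS is not VIIS, so this is illustrative.

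**How often the tests disagree.** Assume independent subjects, P(−1)=2/3, P(0)=1/3.
- P(k=4) = 15 × 16/729 = 0.329; P(k=5) = 6 × 32/729 = 0.263; P(k=6) = 64/729 = 0.088.
- Met by t-test: 0.329 + 0.263 = 59%, or 68% if k=6 counts.
- Met by exact test: k=6 only, 9%.

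**Direction of the effect.** Of all 742 sets of six changes in −4 to +2 with a negative mean, 124 are significant by t-test but not by an exact test, 80 by both and 534 by neither; four have identical changes, so t is undefined. No exact test is significant where a defined t-test is not. The asymptotic test is so in one set, (−4, −1, −1, −1, −1, 0): t-test p=0.062, asymptotic p=0.034.

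**False 'met' rate.** I enumerated all −1/0/+1 outcomes with P(+1)=P(−1) from 0.10 to 0.45, counting only the negative direction that the rule requires. The rate is 0.1–3.2% for the t-test (maximum 3.0% if identical changes do not count) and at most 0.8% for the exact test.

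**The case against.** The strongest reply is that little depends on this p-value. Protocol 10.4 bases the efficacy conclusion on Part 2. Protocol section 10 starts Part 2 on safety, a mean active change near or above 0.5, and recruitment feasibility. SAP 8.2 itself demotes significance to an additional index and requires a rationale for any change. This stands, and it limits the consequence to the Part 1 label. It does not remove the point, because 10.1 still declares the primary endpoint met or not met by significance, and a rationale written after looking is not pre-specification.

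A reader might infer that the replacement could never reach p<0.05 once a subject is unchanged. The documents do not support that. The 0.0625 floor belongs to exact two-sided tests with six or fewer subjects. On the 5/1 data an asymptotic signed-rank test gives 0.025 and an exact one-sided test 0.031. With seven treated and one unchanged, the exact two-sided test can reach 0.031. SAP 8.2 names none of these versions, so all remain open.

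A reader might also infer a route to false positives. The enumeration shows little of one: an exact swap never rescues a failed, defined t-test, and the asymptotic swap does so in one set of 742.

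Finally, the SAP sets no date for the decision. That it would come after unblinding is an inference from the treated-only model and the unblinded analysis, not something the SAP states.

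**Conclusion.** The point holds in a limited form and should be corrected. SAP 8.2 permits a data-driven replacement of a primary analysis that 10.1 has already fixed, and the admissible tests give opposite verdicts on plausible results: 0.004 against 0.0625 for five improvements of six, and 0.025 against 0.125 for four of six. Under the assumed 2/3 response, the chance of 'met' falls from 59% (or 68%) to 9% if an exact test is substituted. The harm is an undefined verdict, and a conscientious swap that discards a real result.

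This rests on six treated subjects, two-sided alpha 0.05, whole-grade changes and independent subjects. The t-test also stands in for the MMRM; a covariate, missing visits or another covariance structure would change the model's p-value. The efficacy claim and the start of Part 2 do not depend on it.

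**What to change.** Before Part 1 unblinding, add to SAP 8.2:

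*This substitution does not apply to the primary analysis; the sequence in 10.1 decides whatever the observed distribution, at two-sided alpha 0.05. If all Visit 8 changes are identical, so that the model and t-test are undefined, the exact two-sided sign-flip test decides. Otherwise the exact sign-flip test of the Visit 8 changes is supportive only.*

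State in 10.1 that, for the t-test or the exact fallback, 'met' means p<0.05 with a negative mean change.

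The provision for identical changes is needed because locking 10.1 alone would leave six equal improvements without a verdict, which is 8.8% of trials under the 2/3 assumption; the exact test gives p=0.031 there. A sponsor who prefers an exact test throughout can instead name it in 10.1 before unblinding and reword the success rule for it.

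The cost is a few sentences in the SAP. The sponsor gives up a choice after seeing the data. The separate provision in 8.2 for adding covariates is not addressed by this change.
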